11.2.2. Patient Disposition

The number of patients enrolled, treated, discontinued from study drug, and those with major protocol deviations will be counted by cohort. The primary reason for study drug discontinuation will be summarized according to the categories in the eCRF. The end of study status (alive, dead, withdrew consent, or lost to follow-up) at the data cutoff date will be summarized using the data from the eCRF.

Major protocol deviations will be summarized and listed by each category.

11.2.3. Demographics and Other Baseline Characteristics

Demographic and other baseline characteristics will be summarized by cohort in the Safety Population using descriptive statistics. Continuous variables include age, weight, vital signs, time

since initial tumor diagnosis, time since metastatic disease; categorical variables include sex, age group (< 65 versus ≥ 65 years), race, disease stage, ECOG-PS, prior line of therapy in the metastatic setting, and geographic region.

11.2.4. Prior and Concomitant Therapy

Concomitant medications will be assigned an 11-digit code using the WHO-DD drug codes. Concomitant medications will be further coded to the appropriate anatomical therapeutic chemical (ATC) code indicating therapeutic classification. Prior and concomitant medications will be summarized and listed by drug and drug class in the clinical study report (CSR) for this protocol. Prior medications will be defined as medications stopped before the first dose of study drug. Concomitant medications will be defined as medications that (1) started before the first dose of study drug and were continuing at the time of the first dose of study drug, or (2) started on or after the date of the first dose of study drug up to 30 days after the patient's last dose. A listing of prior and concomitant medications will be included in the CSR of this protocol.

11.2.5. Efficacy Analyses

No formal hypothesis testing is planned in this Phase 1b study.

For solid tumors other than prostate cancer, tumor assessment based on investigator assessment according to RECIST v1.1 will be used to calculate ORR, DCR, PFS, and DOR, as well as timepoint estimate PFS-6m. Overall survival (OS) and OS-6m will be summarized as well. For patients with ovarian cancer, tumor response may also be assessed by investigators based on GCIG criteria which use carcinoma antigen-125 (CA-125) in combination with RECIST v1.1 ([Appendix 9](#)).

For patients with prostate cancer, PSA and tumor lesions will be evaluated together to determine the tumor response according to PCWG2 criteria ([Appendix 10](#)).

ORR is defined as the proportion of patients who have a best overall response (BOR) of CR or PR, where BOR is defined as the best response recorded from the first dose of study drugs until data cut, disease progression, or start of new anti-neoplastic treatment. Binomial exact 90% and 95% confidence intervals will be calculated for ORR in each cohort.

DCR is defined as the proportion of patients with BOR of CR, PR, and SD. It will be summarized similarly as ORR.

PFS is defined as the time from the date of the first dose of study drugs to disease progression or death, whichever occurs first.

PFS censoring rule will follow FDA *Guidance for Industry, Clinical Trial Endpoints for Approval of Cancer drugs and Biologics* (2007). Patients who have a clinical determination of progression should undergo imaging and laboratory assessments, if possible, to correlate radiographic findings with the clinical findings. Data for patients without disease progression or death by the time of analysis will be censored at the time of the last tumor assessment. Data from patients who are lost to follow-up prior to documented disease progression will be censored at the last tumor assessment date when the patient is known to be progression-free. More details will be given in the SAP.

DOR is defined as the time from the date of the earliest documented response to disease progression or death for any cause, whichever occurs earlier. Only responders will be included in the DOR calculation.

OS is defined as the time from the date of the first dose of study drugs to death.

Time to event variables PFS, DOR, and OS will be estimated using the Kaplan-Meier (KM) method. KM estimates of PFS, DOR, and OS will be plotted over time. Median PFS, DOR, and OS, if estimable, in each cohort will be presented, along with their 2-sided 95% confidence intervals using a generalized Brookmeyer and Crowley method. The PFS-6m and OS-6m, defined as the percentages of patients in the analysis population who remain alive and progression free at 6 months (or alive at 6 months for OS-6m), will be estimated using the KM method along with the corresponding 95% confidence interval constructed using Greenwood's formula.

Maximum tumor shrinkage per patient will be presented in waterfall plots.

Primary analysis of efficacy endpoints will be carried out based on the maturity of the efficacy and safety data in the study, which will be determined by the sponsor.

ORR and DCR will be summarized in the specified subgroups: sex, age group (< 65 versus \geq 65), race, disease stage, ECOG-PS (0 versus 1), number of prior lines of therapy, and geographic region.

11.2.6. Pharmacokinetic Analyses

For patients who contributed full PK profiles up to 48 hours on Cycle 1 Day 1, and up to 6 hours on Cycle 1 Day 15 (Section 8.3.1), the following PK parameters will be derived: C_{max} , T_{max} , $t_{1/2}$, apparent clearance of the drug from plasma (CL/F), and V_z/F .

For the remaining patients, population PK analysis may be carried out for pamiparib to include plasma concentrations from this study in an existing model. PK parameters such as C_{min} will be summarized, and additional PK parameters such as CL/F and AUC may be derived from the population PK analysis if supported by data. Population PK analysis may be reported separately from the final CSR.

Trough and/or peak plasma concentrations of TMZ will be summarized and compared with appropriate historical control.

Exposure-response (efficacy or safety endpoints) analysis may be carried out if supported by data.

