7.8.1. PK of Pamiparib

To better characterize the pamiparib PK profile prior to TMZ administration, the first 15 patients enrolled into the study in dose escalation will undergo intensive PK sampling starting on Day -2 at the following timepoints: pre-dose (within 30 min prior to dose), 30 minutes (± 5 min), 1 hour (± 15 min), 2 hours (± 30 min), 4 hours (± 30 min), 6 hours (± 30 min); 24 hours (± 2 hours) post-dose on Day -1; and 48 hours (± 2 hours) post-dose on Day 1 as detailed in Table 2 of [Appendix 1](#).

After 15 patients have completed intensive PK sampling, all other patients enrolled in dose escalation and expansion will have PK samples collected at the following timepoints: pre-dose (within 30 min prior to dose), 1 hour (± 15 min), 2 hours (± 30 min), and 4 hours (± 30 min) post dose on both Cycle 1 Day 1 and Cycle 1 Day 15. The time of study drug administration on the day prior to Cycle 1 Day 15 must be recorded on the eCRF. Details concerning collection and handling of the PK plasma samples will be provided in the Study Manual.

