8.3.1. PK Intensive Visit (Day -2 to Day 1) (Dose Escalation Cohort ONLY)

To better characterize the pamiparib PK profile prior to TMZ administration, the first approximately 20 patients enrolled into the study will undergo intensive PK sampling starting on Day -2 as detailed in [Appendix 1 Table 2](#).

Once 20 patients have completed the pamiparib PK intensive sampling, the remainder of patients will undergo limited PK sampling as detailed in [Appendix 1 Table 1](#). Any modifications to assignment of PK sampling schedule may be implemented following discussion with the Medical Monitor.

Patients who participate in the PK intensive sampling will have baseline assessments performed on Day -2 before pamiparib dosing rather than on Day 1 as detailed in [Appendix 1 Table 2](#).

Note: The collection of blood for the pamiparib PK 48-hour post-dose timepoint must occur **prior** to the administration of pamiparib and TMZ on Day 1.

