17. Blood tumor antigens such as CA-125 for ovarian cancer and PSA for castration-resistant prostate cancer will be tested during screening and every 8 weeks ± 7 days after the first dose of pamiparib in local laboratories. The CA-125 responses must be confirmed and maintained for at least 28 days. Patients can be evaluated according to CA-125 only if they have a pretreatment sample that is at least twice the upper limit of the reference range and within 2 weeks before starting the treatment.
18. Testing will be performed by local laboratory at screening and as clinically indicated and will include HBV/HCV serology (hepatitis B surface antigen, hepatitis B surface antibody, hepatitis B core antibody, and HCV antibody) and viral load assessment (HBV DNA and HCV RNA).
19. Concurrent medications will be collected during screening and on the first day of study. Changes to Concurrent medications will be collected during subsequent clinic visits.
20. Pharmacokinetic (PK) samples will be collected at the following timepoints: For pamiparib: ≤ 30 min before pamiparib and TMZ dosing, 1 (± 15 min), 2 hours (± 30 min), and 4 hours (± 30 min) after pamiparib dose on Cycle 1 Day 1 and Cycle 1 Day 15; For TMZ: on Cycle 1 Day 1 and Day 7 at ≤ 30 min before dosing and 1 hour (± 15 min) after TMZ dose.
21. Blood samples must be collected at screening or on Day 1 for the assessment of germline *BRCA* and/or other mutation analysis (8 ml). In addition, two blood samples (10 mL each) must be collected for plasma markers (e.g., CNA), TMZ treatment, and PARP inhibition **before** study treatment on Day 1 and

Day 15, and at the EOT visit (unless one had been collected within 14 days). Instructions for the processing, storage, and shipping of samples will be provided in the Study Manual.

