6. A computed tomography (CT) or MRI scan of the thorax, abdomen, and pelvis plus other relevant evaluations as appropriate will be performed.
7. ECGs will be performed in triplicate on Day -2 within a 5-minute window **prior** to pamiparib PK assessments. ECGs for each patient should be obtained from a calibrated machine provided for the study and the same machine must be used for all ECG assessments on Day -2. Triplicate ECGs will be sent to a central reader.
8. Pamiparib PK samples will be collected at the following timepoints: For pamiparib: ≤ 30 min before dosing on Day -2 and post-dose at 30 min (± 5 min); 1 hour (± 15 min); 2 hours (± 30 min), 4 hours (± 30 min), and 6 hours (± 30 min), 24 hours (± 2 h) on Day -1, and 48 hours (± 2 h) on Day 1.
9. Pamiparib dosing must occur after the collection of the 48-hour post-dose PK sample on Day 1.
10. Collection of archival tumor tissue for purpose of biomarker analysis is highly recommended. Specific instructions for tissue collection and shipment are provided in the Study Manual.
11. In the absence of archival tumor tissues, a fresh baseline biopsy of a tumor lesion is highly recommended. **Any tissues taken during pre-screening period will not be re-collected during baseline.** An optional biopsy for biomarker analysis after treatment on Cycle 1 and if agreeable, also on Cycle 1 Day 15, and EOT is highly recommended. Optional biopsy will also be taken at the EOT visit for the patients who have confirmed disease progression during the study from accessible tumor sites to obtain samples to explore resistance mechanisms. If feasible, any follow up biopsy should be ideally taken from the same tumor lesion as the baseline biopsy. Written patient consent is required for fresh tumor biopsies. Fresh biopsies should be limited to readily accessible tumor lesions (e.g., skin, peripheral lymph nodes, lung, liver or internal lymph node metastases which can be readily accessed using CT guidance). If performed, a tissue cylinder should be obtained that has proper size for histological examination and biomarker analysis.
12. TMZ dosing must occur after the collection of the 48-hour post-dose PK sample on Day 1.
13. TMZ PK samples will be collected at the following timepoints: pre-dose (within 30 min prior to dose) and 1 hour (± 15 min) post dose.

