6.3.6 Pharmacokinetic Endpoints

For subjects in BGB-290 PK intensive group who contributed full PK profiles up to 48 hours postdose of Cycle 1 Day 1, and up to 6 hours on Cycle 1 Day 15, the following PK parameters

will be derived: C_{max} , C_{2h} , T_{max} , $T_{1/2}$, AUC_{0-4h} , AUC_{0-inf} (Day 1), AUC_{last} , apparent clearance CL/F , and V_z/F (Day 1).

For the remaining subjects, PK parameters such as C_{min} will be summarized. Population PK analysis may be carried out to include plasma concentrations from this study in an existing model, and additional PK parameters such as apparent clearance of the drug from plasma (CL/F) and AUC may be derived if supported by data. Population PK analysis may be reported separately from the final CSR.

Trough and/or peak plasma concentrations of TMZ will be summarized and compared with appropriate historical control.

Exposure-response (efficacy or safety endpoints) analysis may be carried out if supported by data.

A summary of concentration for pamiparib (sparse and intensive sampling separately) and TMZ, and PK parameters for pamiparib, listings for concentration (pamiparib and TMZ separately) and parameters for pamiparib and figures of concentration vs time for intensive pamiparib PK sampling will be provided.

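### The rule for deriving pamiparib PK parameters names the wrong dose in the SAP, asks for a Day 15 time beyond the scheduled samples, and rests on an intensive group given as both 15 and about 20 patients

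*Protocol*

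**What the plan says.** Both documents restrict the full set of pamiparib parameters to patients who meet a joint sampling condition. Protocol 11.2.6 requires "full PK profiles up to 48 hours on Cycle 1 Day 1, and up to 6 hours on Cycle 1 Day 15" and cites Section 8.3.1. SAP 6.3.6 applies the rule to the PK intensive group and words it as "full PK profiles up to 48 hours postdose of Cycle 1 Day 1, and up to 6 hours on Cycle 1 Day 15". The SAP also attaches the label Day 1 to AUC0-inf and to Vz/F.

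The sampling itself is set out elsewhere in the Protocol:

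- **Intensive profile.** Appendix 1 Table 2 (note 8) starts it at the Day -2 dose, with samples before dosing and at 0.5, 1, 2, 4 and 6 hours, then "24 hours (± 2 h) on Day -1, and 48 hours (± 2 h) on Day 1". Section 8.3.1 and notes 9 and 12 of that table place the 48-hour sample before pamiparib and TMZ are given on Day 1.
- **Day 15.** The last pamiparib sample is at "4 hours (± 30 min) post dose on both Cycle 1 Day 1 and Cycle 1 Day 15" in Section 7.8.1, and at "4 hours (± 30 min) after pamiparib dose on Cycle 1 Day 1 and Cycle 1 Day 15" in Appendix 1 Table 1, note 20.
- **Group size.** Section 7.8.1 says "the first 15 patients enrolled into the study in dose escalation will undergo intensive PK sampling starting on Day -2"; Section 8.3.1 says "the first approximately 20 patients enrolled into the study will undergo intensive PK sampling starting on Day -2". The title of Appendix 1 Table 2 also gives about 20.

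**The concern.** An eligibility rule for a derived parameter should point to samples that the schedule collects, and the label should name the dose that produced them. Here neither holds throughout.

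Characterising the PK of pamiparib and TMZ is the only secondary objective. The Day -2 profile exists to describe pamiparib before TMZ is added. If its clearance, half-life and volume are reported under Day 1, single-agent values appear as values from the first combination dose, and the reference for judging any effect of TMZ is blurred. If an analyst instead applies the joint condition strictly, nobody who followed the schedule qualifies. Either way, someone has to depart from the written plan after the data are in hand.

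**Working it through.** No power or sample-size formula applies, and neither document derives 15 or 20. The check sets the required times beside the scheduled ones.

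| Item | Required by Protocol 11.2.6 / SAP 6.3.6 | Scheduled in 7.8.1, 8.3.1 and Appendix 1 |
|---|---|---|
| 48 h profile | Tied to Cycle 1 Day 1 (SAP: after that day's dose) | After the Day -2 dose; the 48 h sample is taken on Day 1 before dosing |
| Last sample after the Day 1 dose | 48 h (SAP wording) | 4 h |
| Last sample on Day 15 | 6 h | 4 h |
| Intensive group | Not stated | 15 (7.8.1); about 20 (8.3.1, Table 2 title) |

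**Step 1: which dose the 48 h profile belongs to.** Protocol 6.1.1.3 gives pamiparib twice daily, about 12 hours apart. Once that dosing starts on Day 1, further doses fall at about 12, 24 and 36 h, so a single-dose 48 h profile cannot start there. The profile belongs to Day -2. SAP 6.2.1 uses the same convention: the intensive group's first pamiparib dose is Study Day -2, and Cycle 1 Day 1 is the first combination dose. By the SAP's own definition, Day 1 is the wrong label.

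**Step 2: why the anchor matters for these parameters.** Protocol 1.5.1 gives a terminal half-life of about 13 h (range 5.4 to 34 h). Number of half-lives covered = t / t½. Fraction of concentration left = 2^(−t/t½), assuming simple exponential decline.

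| t | t½ = 5.4 h | t½ = 13 h | t½ = 34 h |
|---|---|---|---|
| 4 h | 0.74 half-lives, 60% left | 4/13 = 0.31, 81% left | 0.12, 92% left |
| 6 h | 1.11, 46% left | 6/13 = 0.46, 73% left | 0.18, 89% left |
| 48 h | 8.89, 0.2% left | 48/13 = 3.69, 7.7% left | 1.41, 38% left |

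At the typical half-life, the Day -2 profile can support half-life, AUC0-inf, CL/F and Vz/F; at the slow end of the range even 48 h is short. Samples to 4 h or 6 h after a Day 1 or Day 15 dose cannot support them.

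**Step 3: Day 15.** Two places end pamiparib sampling at 4 h. The only scheduled 6 h pamiparib sample is on Day -2. Section 7.5, however, lists triplicate ECG times for Cycle 1 and Day -2 that include 6 h, and ties those ECGs to the pamiparib PK assessments. Appendix 1 schedules triplicate ECGs on Days 1 and 15. So Section 7.5 suggests a 6 h PK time in Cycle 1 that the PK sections do not contain.

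**Step 4: who is sampled on Day 15.** Section 7.8.1 gives the Day 1 and Day 15 samples to all other patients once the intensive group is complete, and Section 8.3.1 gives limited sampling to the remainder. Note 20 of Table 1 states no such restriction. Whether intensive patients have any Day 15 pamiparib samples is therefore not settled.

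**Step 5: group size.** Section 7.8.1 stops intensive sampling once 15 patients are complete; Section 8.3.1 stops it once 20 are complete. The gap is 20 − 15 = 5 patients, and the word approximately does not close it.

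**The case against.** The strongest reply is that a competent analyst would find the right samples anyway. A 48 h profile is collected. Protocol 11.2.6 cites Section 8.3.1, whose title spans Day -2 to Day 1, and the 48 h sample is in fact drawn on Cycle 1 Day 1. The Protocol phrase can fairly be read as the day of the draw. This stands: in the Protocol the fault is loose wording. It does not rescue the SAP, which says postdose and repeats the Day 1 label on two parameters.

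A reader might infer that the schedule never provides a 48 h profile, or that a 6 h Day 15 sample is certainly absent. The documents do not support either. The first overlooks the Day -2 profile. The second overlooks the 6 h ECG time in Section 7.5, which makes this a conflict between sections and leaves open which is right.

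A reader might also infer that sites cannot tell how to sample patients 16 to 20, or that precision is materially at stake. Intensive sampling is confined to dose escalation, the current Schedule of Assessments already states an expansion dose, and Section 8.3.1 allows changes to sampling assignment after discussion with the Medical Monitor. The practical question is probably past. PK is summarised descriptively with no hypothesis test, so no decision turns on 15 against 20.

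Finally, the SAP says that PK details may be placed in a separate plan, and its PK Analysis Set needs only one concentration, so concentration summaries do not depend on this rule. That limits the damage to the derived parameters. It does not correct the text.

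**Conclusion.** The point holds as an inconsistency to be corrected before the PK analysis. Three things are wrong as written: the SAP attributes the 48 h profile and two parameters to the first combination dose instead of the Day -2 pamiparib-alone dose; both documents require a Day 15 time 2 hours beyond the last scheduled sample (6 − 4); and the intensive group has two sizes, 5 patients apart.

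Read strictly, no patient who followed the schedule meets the joint condition. That is a consequence of the wording and should not be taken as a finding that data are missing: the Day -2 samples are in the schedule and the parameters can be derived from them. The conclusion assumes that those samples were taken as scheduled. It does not assume an answer on whether 4 h or 6 h applies on Day 15, or on whether the intensive group was sampled that day; the documents leave both open.

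The effect is confined to a secondary PK analysis. The ORR and DLT analyses are unaffected.

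**What to change.** In Protocol 11.2.6 and SAP 6.3.6:

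1. Derive Cmax, Tmax, half-life, AUC0-inf, CL/F and Vz/F from the Day -2 profile alone, and label them Day -2, single dose, pamiparib alone.
2. Drop the joint Day 15 condition. Single-dose parameters need no Day 15 sample, and keeping the condition could still empty the set if intensive patients were not sampled then.
3. Summarise Day 15 parameters separately (for example Cmax and AUC0-4h, which the SAP already lists) for every patient who has the Day 15 samples actually scheduled.

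Reconcile Protocol 7.5, 7.8.1, 8.3.1 and both tables of Appendix 1 on the last Day 15 PK time, on whether the intensive group is sampled on Day 15, and on one intensive-group size. If the number has already been reached in practice, state the number achieved.

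The cost is editing. The single-dose parameters need no new samples. The Day 15 summary also needs none, provided it is defined by the samples that were scheduled and taken.

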11.2.7. Exploratory Analyses

Exploratory endpoints include blood and tumor biomarkers and will be analyzed using the Safety Population. The correlation of predictive biomarkers with efficacy endpoints for study treatment will be explored.

11.3. Safety Analyses

Safety will be assessed by monitoring and recording of all AEs graded by NCI [CTCAE v4.03](#). Laboratory values (CBC, clinical chemistry, coagulation, and urinalysis), vital, physical exams, and ECGs findings will also be used in determining the safety.

11.3.1. Extent of Exposure

Extent of exposure to each study drug will be summarized in each cohort descriptively as the number of cycles received (number and percentage of patients), duration of exposure (days), cumulative total dose received per patient (mg), dose intensity, and relative dose intensity.

The number (percentage) of patients requiring dose reductions, dose delay, and drug discontinuation due to AEs will be summarized by dose level. Frequency of dose reduction and dose delay will be summarized by categories.

Patient data listings will be provided for all dosing records and for calculated summary statistics.

11.3.2. Dose-limiting Toxicity

Dose-limiting toxicity in the DLT evaluation period will be used to determine the dose and schedule of pamiparib plus TMZ in the expansion cohorts. The DLT events will be summarized descriptively at each combination dosing level in the DLT evaluable Population.

